3. STUDY DESIGN

Overview: This study will investigate NAC's biological signatures in adolescent NSSI, testing whether a meaningful change in measurable biomarkers (GSH and GLU) can be achieved following a 4-week course of NAC treatment. We will recruit 36 adolescents and young adults aged 16-24 years. They will be assigned to one of 3 groups (double-blinded): a low-dose NAC group (3600 mg/day), a high-dose NAC group (5400mg/day), and PBO. This design will allow us to confirm acute biological changes, select the optimal dose for achieving biological effects, and examine dose/concentration-response relationships with respect to biological markers and PK.

Primary outcome measure:

- 1) GSH concentration in ACC.

Secondary outcome measures:

- 1) Reduced-to-oxidized GSH ratio in blood (GSH/GSSG)
- 2) Glu concentrations in ACC
- 3) Tolerability of NAC as measured using a side effects checklist
- 4) Pharmacokinetics of NAC and its metabolites, CYS and GSH
- 5) Antioxidant protein levels (catalase and heme oxygenase-1 [HO-1]) for which previous studies have shown increases following NAC treatment
- 6) GABA concentrations in ACC. Our pilot study found a significant increase in

GABA levels after 28 days of oral NAC (6000 mg/day) ([name] et al. 2018).

7) Functional connectivity between amygdala and insula. Our pilot study showed that after treatment with oral NAC (3600 mg/day), participants with NSSI showed an increase in amygdala functional connectivity in a cluster that included the bilateral insula.

Table 1 - Participant study duration:

Day 0 (in-person or video conference)	3 hours
Day 1 (in-person)	4 hours
Days 2-27 (at home)	Study drug taken at home (5 capsules in the morning, 4 capsules in the evening)
Days 7 and 21 (online forms at home)	0.5 hours
Day 14 (+/- 2 days) (in-person or video conference)	0.5 hours
Day 28 (+/- 3 days) (in-person)	3-8 hours (shorter protocol during COVID-19 pandemic)
Total	11-16 hours over 4 weeks

Duration to enroll all participants: 2 years

Duration to complete all study procedures, including analysis: 3 years

Study locations:

- 1) Ambulatory Research Center
Department of Psychiatry and Behavioral Sciences
University of Minnesota, Twin Cities Campus
[name]
[name]
[name]
- 2) Research in Adolescent Depression Lab (RAD Lab) @ Riverside Park Plaza
University of Minnesota Medical School
[name],
[name]
- 3) Center for Magnetic Resonance Research
Department of Radiology
University of Minnesota, Twin Cities Campus
[name]
[name]

Study intervention description: NAC is a natural product that may have promise for treating NSSI in adolescents. NAC is the N-acetyl derivative of the amino acid L-

cysteine and a precursor of the antioxidant glutathione. It can be found in health food stores with other nutritional and dietary supplements. The bioavailability and pharmacokinetic (PK) properties of intravenous (IV) and oral NAC have already been established in humans (Holdiness 1991).

Study intervention handling: The SW854 product will be provided to the Investigational Drug Service (IDS) Pharmacy by the company Swanson Health Products. UMN IDS will supply and prepare matching placebo, as well as handle all NAC and placebo allocation and dispensing. All participants, family members, and the entire research team will be blinded to active NAC versus PBO assignment. If there are any leftover capsules not taken by a participant, these will be returned to IDS, recorded and disposed of according to University of Minnesota IDS procedures.

Randomization and Double-Blind. Participants who meet criteria for entry into the study (based on the online screen and the clinical interview) and who consent to participate will be randomized to active NAC high dose vs. active NAC low dose versus PBO (1:1:1). We will implement an adaptive randomization procedure called minimization. The purpose of the procedure is to ensure that the 3 groups are similar with respect to key demographic and clinical variables (such as age, NSSI severity, medication use). The study statistician will use this participant information to assign a blinded randomization group (A, B, or C) using the minimization procedure.

The study statistician will then pass the blinded group assignment to the research pharmacy, IDS. Before the first participant is randomized, IDS will randomly assign “NAC high” “NAC low” and “PBO” to the letters A, B, and C; this assignment (of treatment name to treatment letter) will not be communicated to anyone outside of IDS until the study is complete and the study team is ready to break the blind. All participants, family members, and the entire research team (including the study statistician) will be blinded to high NAC versus low NAC versus PBO assignment. The IDS pharmacist will be authorized to break the blind on an individual participant’s treatment assignment in the event of that participant’s medical emergency. See Section 6.2.2 for additional details.

4. SELECTION AND ENROLLMENT OF PARTICIPANTS

4.1 Inclusion Criteria

Participants must meet all of the following inclusion criteria in order to participate in this study:

- 1) 16-24 years old
- 2) Female assigned at birth.
- 3) Current frequency of at least one NSSI episode in the past 2 months
- 4) ≥ 5 past episodes of NSSI with significant tissue damage (e.g. skin is broken or bruised, and/or scars resulted from the injury)

- 5) Psychotropic medications are dose-stable for 1 month.
- 6) Ability to understand study procedures and to comply with them for the entire length of the study.

4.2 Exclusion Criteria

All candidates meeting the following exclusion criteria will be excluded from study participation. Candidates will be screened for these criteria prior to consent. If it is found that participant meets exclusion criteria after consent (i.e. at Visit 1 Clinical Assessment) participants will be removed from the study or given the necessary time to meet eligibility before continuing with study activities.

- 1) Any MRI contraindications (e.g. metal plates, claustrophobia, braces, implanted devices)
- 2) Male assigned at birth.
- 3) Any current serious medical illness as defined by medical history
- 4) Current Substance Use Disorder (except Tobacco Use Disorder, mild cannabis use disorder, mild alcohol use disorder, or SUD in early remission with abstinence ≥ 3 months)
- 5) Primary psychotic disorder (e.g. schizophrenia, schizoaffective disorder, schizopreniform disorder)
- 6) Neurodevelopmental disorder such as mental retardation or autism
- 7) Changes in psychotropic medications in past 1 month
- 8) Taken NAC or glutathione on a regular basis in the past 6 months
- 9) Currently pregnant, planning to become pregnant, currently breastfeeding, or unwillingness to use contraception throughout the study.
- 10) Allergy/sensitivity to N-acetylcysteine.
- 11) Inability or unwillingness of individual or legal guardian/representative to give written informed consent.

Rationale: Males are excluded for two reasons. First, since there is significant sexual dimorphism of brain circuitry that emerges during the adolescent period, given the small sample, we want to minimize sex-related variability. Second, the prevalence of NSSI is higher in females. In the NAC/NSSI pilot study conducted by our lab, 40 females and 1 male enrolled. As a result, the single male needed to be excluded due to being the only one.

4.3 Study Enrollment Procedures

Our goal is to have completed data for analysis on 36 participants, with the expectation of most of these coming from the University of Minnesota Psychiatry Department research registry and Fairview in-patient units (referrals and flyers). Participants will also be recruited within the local community using flyers and social

media marketing. We expect to consent up to 80 people and enroll up to 46 participants with the expectation of up to 20% attrition due to participant withdrawal.

Recruitment

We will pursue the following procedures for candidate recruitment:

- 1) We will contact participants from our prior research outreach efforts who were either ineligible, screened out or participated in previous research, and who had indicated a willingness to be contacted in the future.
- 2) We will use the research participant registry based in the University of Minnesota Psychiatry outpatient clinic.
- 3) We will utilize the M Health clinical data repository of those Fairview patients elected to participate in University of Minnesota research. Fairview Research Services provides a service that identifies patients in this database that fit eligibility criteria and sends a letter to the patient informing them about the research opportunity.
- 4) We will screen electronic medical records of adolescents with a history of self-injurious behavior treated in the clinics and hospital services of the University of Minnesota, Medical Center and Masonic Children's Hospital. We will only look at the records of those patients who have not opted-out of having their medical records used for research on the Consent for Services form they complete at intake. When potential cases are identified, we will contact the treating physician to discuss the patient and whether they might be suitable for consideration for the study. If yes, we will ask the physician (or they physician may choose to delegate this to another member of the treatment team) to approach the parent or guardian about the study. The physician (or delegated treatment team member) will let parents know that their daughter may be eligible to participate in a research study being conducted at the University of Minnesota, and will ask the parent or guardian whether they would like to be contacted by the research team to learn more about the study. The physician (or delegated treatment team member) will explain that participation is completely voluntary and in no way related to the treatment for their daughter. Information about study opportunities will also be provided for potential participants on a research board on the unit. The board will (a) post information about the study, (b) provide small cards with study information that parents can take home.
- 5) We will use the Fairview research recruitment mailing process. Potential participants are identified, based on protocol eligibility criteria, from a clinical data repository that houses the records of over 2 million patients. Once

identified, Fairview mails the IRB approved study recruitment letter to its patients on behalf of the researcher.

- 6) We will post advertisements in the community via flyers and local newspapers. We will use a Quick Response (QR) code on all printed and digital materials which will direct potential participants to a REDCap survey. The REDCap survey asks for contact information, birth date of the potential participant, and also if they have ever self-injured. The REDCap survey and responses are to be maintained by the study team.
- 7) We will advertise through the internet, social media (Facebook, Pandora, Tumblr, etc.) and community outlets about our study and create an informative space about research opportunities and information about depression, self-harm and mental health for adolescents and young adults. Social media accounts for this research lab (RAD Lab) will be used for this study, as well as accounts for the University of Minnesota Department of Psychiatry managed by the Research Recruitment Specialist working on behalf of research staff for recruitment. Social media and internet traffic will be directed to a HIPAA compliant REDCap screening form (survey) on the website of our research lab (radlab.umn.edu) which will capture screening information for self-selected study candidates interested in more information and/or participation.
- 8) We will use advertisements on digital media platforms to reach our research population via demographic and key words. An interested individual's click will bring them to a REDCap survey. The REDCap survey asks for contact information, birth date of the potential participant, and also if they have recently self-harmed.
- 9) We will meet regularly with clinical groups affiliated with the University of Minnesota that are involved in the treatment of the target population to build awareness of the study and enhance referrals.
- 10) We will maintain a social media presence to promote the study and enhance visibility to the community. A coordinating website "radlab.umn.edu" will be used to describe participation information, including inclusion and exclusion criteria and amount of time to complete study. This information will also be posted on the University of Minnesota Department of Psychiatry website "z.umn.edu/findastudy". The website and media pages will provide study team contact information and IRB approval number. Media sites will be compliant with HIPAA: no identifying information will be collected and potential participants will be advised to contact the research team directly via phone or email for additional information about this study. The lab will include the following disclosure: "Disclaimer: The information on this site is

not intended or implied to be a substitute for professional medical advice, diagnosis or treatment. All content, including text, graphics, images and information, contained on or available through this website, is for general information purposes only. Please contact your physician to form a plan that addresses you or your child's specific needs" wherever space is allotted."

- 11) We will make regular presentations about the research to community organizations including neighborhood groups, parent groups, and church groups.
- 12) Participants will be recruited through the Research Experience Participation (REP) program in the Psychology Department at the University of Minnesota. Study information will be available on the REP website. Research staff may introduce the study in relevant UMN courses and emails with study information may be distributed in relevant UMN courses.
- 13) Descriptions of the study will also be posted on research study websites, like ClinicalTrials.gov and StudyFinder.
- 14) We will be recruiting for the study at the Minnesota State Fair Driven to Discover Research Facility (D2D) at a recruitment booth for our research lab. We will have flyers and brochures about the study at the booth. For parents or guardians who tell us they have a daughter in our study age range (16-18), or the individual themselves (18 to 24) we will encourage them to complete a permission to contact form to indicate their interest in being contacted about the study and gather their contact information using a secure REDCap form. We will be giving away small prizes for those who sign their daughter up to be contacted.

Sites for Recruitment:

- 1) UMN Psychiatry Clinic: Potential participants will be contacted from the clinic registry. In addition, a flyer will be posted outside of this clinic where potential participants will self-identify and potentially contact research staff to inquire more information.
- 2) Fairview/M Health: Fairview Health Services will identify potential participants from a clinical data repository then mail an IRB-approved study recruitment letter to their patients on behalf of the research team.
- 3) Community bulletin boards: Flyers will be posted on community boards such as in coffee shops, cafes and community centers, where permission is granted.
- 4) Internet advertisement: Similar advertisements will be posted through internet forums where IRB approved. We will engage BUMP marketing with IRB approved materials for internet advertisement.
- 5) High schools: We will engage local high schools to gauge interest in presentations to students or community groups about health topics related to brain development, adolescent health, self-harm and mental health. We will

also reach out to high school counselors to build awareness and encourage referrals for the research study.

- 6) Clinical groups: We will engage local clinical groups that may see the target population as patients to build awareness and encourage referrals for the research study.
- 7) Community groups: We will engage community groups
- 8) Minnesota State Fair Driven to Discover Research Building: We will have a booth at this building to recruit participants for the research study.

The following recruitment materials are in production and will be used for recruitment. Once finished, copies will be provided to Advarra IRB for approval.

- 1) Flyer (for public display outside outpatient clinic, potential participant self-identify)
- 2) Flyer (for public display outside inpatient clinic, potential participant self-identify)
- 3) Flyer (for public display in community, potential participant self-identify)
- 4) Flyer (for display to clinicians/clinical groups, potential participants identified by clinician)
- 5) Internet advertisement (for public display, potential participant self-identify)
- 6) Letter to Fairview patient (mailed directly to potential participant, identified by Fairview staff via repository)
- 7) Study summary shown to potential participants when accessing online screening form)
- 8) REDCap online screen (automated screening form for potential participant eligibility)

Screening

Screening documentation: A screening log will be kept to record all candidates, reasons for ineligibility or reason for electing to not participate.

Consent

We anticipate to consent up to 80 people. The consent process with study candidates and/or their parent/guardian will be conducted by the research coordinator or principal investigator and will take place at the very first scheduled visit, Day 0, before the clinical assessment. They will receive copies of the parental consent, assent (if applicable), email authorization and HIPAA forms via encrypted email or USPS

mail at least 24 hours before this appointment. The initial consent process will take place with research staff in a previously reserved room within the Ambulatory Research Center (ARC) at the University of Minnesota Department of Psychiatry (F212) Fairview Riverside West Building, or at the Research in Adolescent Depression Lab at the University of Minnesota Medical School, or via video conference. During the initial consent visit staff will review the consent forms highlighting the most salient points such as study title, purpose, procedures, risks, benefits, alternatives, confidentiality, research related injury, voluntariness, and any additional signing/initial blocks such as permission to re-contact in the future and share data outside of this research study. Talk back method will be used during the consent visit to ensure study candidate and/or their parent/guardian (if applicable) are understanding these points. In addition, an approved version of the UCSD Brief Assessment of Capacity to Consent specific to this study will be used with all candidates during the consent process. Candidates that are not able to complete the UBACC or score less than 2 points on each question will not be consented and enrolled into the study. If a potential participant scores 0 or 1 on any question the information pertinent to that question will be reviewed and discussed with the participant. If the potential participant is then able to answer the question in full and research staff determines the potential participant fully understands the material, they will be scored the 2 points and then consented and enrolled. In addition to University and department mandatory consent training for appropriate research staff, all new staff will be trained in consent for this research study including observing the consent process, mock consent and observed for consent process. Throughout the course of the research study, participants will be gauged of their comprehension of scheduled procedures as well as comfort and willingness to complete these procedures by staff at each visit/procedure. All participants participating in this study or their LARs will be required to provide prospective informed consent. This will be completed via remote consent procedures (including e-consent with electronic signatures) which complies with requirements outlined in Title 21 CFR Part 11. We will email the ICF to the participant or LAR via a REDCap link. We will take special precautions to protect confidentiality (e.g. verbally (over video call) provide the participant and/or LAR with a unique code generated by REDCap that will grant access to ICF). The person consenting the participant or LAR will have the same consent discussion via phone or zoom that they would have had in-person (including asking questions to gauge comprehension and answering the participant's or LAR's questions). If the participant or LAR consents, they will complete and electronically sign the ICF (in all appropriate sections) directly in REDCap. Once the ICF (signed & dated by the participant or LAR) is received by the research team, the study team member who explained the study will electronically sign the appropriate signature line with the current date. They will then email a copy of the fully executed ICF back to the participant. They will document the consent process as appropriate. Study procedures will not begin until all aspects of the remote consent process is complete. A copy of the ICF will not be included in the participant's Electronic Health Record.

For those age 16 or 17, parent/guardian consent will be obtained from at least one parent. Parent/guardian consent will be attempted to be obtained from both parents unless one parent is deceased, unknown, incompetent or not reasonably available due to travel or work. Permission will be obtained from someone other than a parent only when that person is a legal guardian of the potential participant. Assent will be obtained and documented from all participants that meet criteria and are willing to consent that are age 16 or 17. Documentation will be obtained by child signing Assent Form (ink or electronic signature if conducted via video conference), along with research staff personnel obtaining consent (ink or electronic signature if conducted via video conference).

Randomization and Double-Blind: Participants that meet criteria for entry into the study based on the online screen and the clinical interview will be randomized to active NAC (low dose versus high dose), versus PBO. We will implement an adaptive randomization procedure similar to stratification called minimization. The purpose of the procedure is to ensure that the 3 groups are similar with respect to key demographic and clinical variables such as age, depression severity, NSSI severity and medication use. These variables will be shared by the research coordinator in a de-identified file with the study statistician, who will use the information to complete the randomization procedure. She will then share the group assignment with IDS. All participants, family members, and the entire research team will be blinded to active NAC versus PBO assignment.

5. STUDY INTERVENTIONS

5.1 Interventions, Administration, and Duration

Study intervention: N-acetylcysteine (NAC); 600mg capsules

NAC is a natural product that may have promise for treating NSSI in adolescents. NAC is the N-acetyl derivative of the amino acid L-cysteine and a precursor of the antioxidant glutathione. It can be found in health food stores with other nutritional and dietary supplements. The bioavailability and pharmacokinetic (PK) properties of intravenous (IV) and oral NAC have already been established in humans (Holdiness 1991).

Dispensing and administration of intervention: Participants will be provided with a 4-week supply of study drug, plus an additional four days, on Day 1 (Visit 2) by the research coordinator. The study drug is a gelatin 0-size capsule, with a dose of 600mg per capsule. Participants will be provided with an extra four-day supply of study drug in case scheduling challenges occur, in order to ensure adequate dosing of study drug at post-dose biological sampling (PK analysis and 7T MRI scan). The research team will request subjects use a paper medication diary (calendar) or complete a survey via REDCap to optimize and track medication adherence. The participant will have the option of which method they would prefer to use (paper or survey). Participants will indicate this preference through the Medication Tracking Preference Form via

REDCap. If they prefer to receive the surveys, the participants will be asked whether they preferred survey delivery via text or email. The online survey will ask the participants to indicate whether they had taken their daily medication in the morning and afternoon. The participant will not be required to use either of the tracking methods, paper or survey. The research coordinator will contact the participants on day 3, 4 or 5 of study participation to check in about their adherence, their chosen method of adherence tracking and experiences with the study drug. They will be instructed to take 5 identical-appearing capsules in the morning and 4 in the evening (5400mg/day, n=12; 3600mg/day, n=12; PBO, n=12; participants in high-dose group will be given 5 active capsules in the morning and 4 active capsules in the evening, participants in low-dose group will be given a mix of active and placebo capsules (3 active capsules and 2 placebo capsules in the morning, and 3 active capsules and 1 placebo capsule in the evening), and the placebo group will receive all placebo capsules. Capsules will be taken by mouth, beginning Day 1(Visit 2) until the final visit (Visit 4; Day 28). Study capsules will be packaged to ensure that the correct capsules are taken at the correct day and time.

NAC side effect reports in published studies of oral NAC have ranged from 81% reporting no side effect (N=1,392)(Tattersall, Bridgman, and Huitson 1983) to no significant between group differences in adverse events (N=75)(Berk et al. 2008). All potential adverse effects from NAC would be acute and reversible.

Oral NAC may cause gastrointestinal adverse effects including nausea, stomach discomfort, diarrhea, and constipation, as well as headache and chest tightness (Behr et al. 1997; Oldemeyer et al. 2003). Adverse effects published resolved with discontinuing NAC demonstrating that effects would be acute and reversible.

For participants that experience adverse effects likely or probably related to study drug the participant will be instructed to diminish their dose by 1 capsule daily until the absence of the adverse effect occurs (i.e. from 9 to 8 to 7, etc., until adverse effect is absent). The goal of tapering down to tolerance will be to allow the participant to remain in the study and tolerate the study drug. If a taper is needed, IDS will re-package the study drug so that the blind is maintained and the correct number of active pills are taken.

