1. STUDY OBJECTIVES

1.1 Primary Objective

To test the hypothesis that oral NAC treatment (but not placebo) will lead to at least a 5% increase in glutathione (GSH) concentrations in the anterior cingulate cortex as measured by magnetic resonance spectroscopy (MRS) in a study of 36 adolescents and young adults with NSSI.

We will test two NAC doses (3600mg and 5400mg). Dose superiority will be defined both by change in GSH and by tolerability. Specifically, the superior dose will be the one which showed capability of achieving the greatest increase in GSH in the ACC as measured by MRS, and where no more than 20% of subjects at that dose discontinue or diminish their dose due to medication adverse effects (See section 5.1 for adverse effects and diminishing dose). (In other words, no less than 80% of subjects at a dose can discontinue or diminish their dose due to adverse effects in order to qualify as a superior dose.)

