7. SAFETY ASSESSMENTS

Safety will be monitored throughout the study. Here we review the risks associated with the study and how we will monitor for these risks.

1. Monitoring for safety related to taking NAC: Side effect reports in published studies of oral NAC have ranged from 81% reporting no side effects (N=1,392)(Tattersall, Bridgman, and Huitson 1983) to no significant between group differences in adverse events (N=75)(Berk et al. 2008). Oral NAC may cause gastrointestinal adverse effects including nausea, stomach discomfort,

diarrhea, and constipation, as well as headache, chest tightness, rash and/or itching. (Behr et al. 1997; Oldemeyer et al. 2003). These problems were reported as resolved following discontinuation of NAC. Adverse effects due to NAC will be monitored using the Side Effects Checklist. Participants who experience adverse effects which are bothersome and which are deemed likely or probably related to study drug will be instructed to decrease their dose by 1 capsule daily until they tolerate the study drug.

2. **Monitoring for safety related to IV catheter placement and blood collection:** The risks of the IV catheter and blood collection include pain at the site, bleeding, bruising, fainting and/or dizziness, superficial phlebitis and infection. These risks will be lessened by using trained technicians to perform this procedure. These potential adverse effects would be acute and reversible.
3. **Monitoring for safety related to suicide risk:** Our study population is at increased risk for suicide attempts (Horwitz, Czyz, and King 2015; Tang et al. 2011; Victor and Klonsky 2014). Suicide risk will be monitored throughout the study in the form of questionnaires and interviews. If a concern for imminent suicide risk is identified, the study team will conduct a more in-depth safety assessment and will engage the adolescent in safety planning. As indicated, this safety assessment and planning may include the parent(s), other family members, treatment team, and / or referral for emergency services / hospitalization. Refer to Supplement IV: RAD Lab procedure on suicide and self-harm behavior risk.

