7.1 Specification of Safety Parameters

Participants will be asked about their health at the mid-study visit (Day 14) and final study visit (Day 28-32). Participants will be instructed to immediately inform the study team if any serious concerns arise with their health during the study.

The Side Effect Checklist (given at baseline, Week 1, Week 2, Week 3 and Week 4) will be used to assess NAC tolerability. If the side effect is marked as "1" (mild, does not interfere with functioning), nothing will be done. If the side effect is marked as "2" (moderate, some interference with functioning), or "3" (severe, functioning is significantly impaired because of side effects), and this rating denotes an elevation from baseline, and is considered to be at least possibly related to study intervention by the Principal Investigator and/or the Independent Clinical Monitor, we will discuss with participant (and, for adolescents under 18, the parent or guardian) to further assess the participant's impairment from the issue and make a joint decision about the risks versus benefits of staying at the same dose versus decreasing the dose. This determination will consider the frequency and the level of impairment associated with the side effect.

The PHQ-9, the BDI-II and the BSSI (given at baseline, Week 1, Week 2, Week 3 and Week 4) will all be used to assess suicide risk. If the participant indicates elevations in suicidal thinking (e.g. marks a “2” on the question about suicidal thinking on the BSSI) this will trigger a deeper safety assessment as described below.

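### Sections 5.1, 7 and 7.1 give conflicting triggers for dose reduction, and Section 1.1 counts the resulting reductions toward the 20% tolerability limit for the superior dose

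*Combined protocol and SAP*

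**What the plan says.** Section 1.1 sets two conditions for the superior dose: the greatest increase in ACC glutathione, and a tolerability limit under which "no more than 20% of subjects at that dose discontinue or diminish their dose due to medication adverse effects". It then adds a pointer: "See section 5.1 for adverse effects and diminishing dose".

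Three places govern reductions.

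- **Section 5.1.** The rule opens "For participants that experience adverse effects likely or probably related to study drug" and continues "the participant will be instructed to diminish their dose by 1 capsule daily until the absence of the adverse effect occurs". There is no severity condition. A following sentence gives the aim as tapering to a tolerated dose so that the participant can stay in the study.
- **Section 7, item 1.** Participants with "adverse effects which are bothersome and which are deemed likely or probably related to study drug will be instructed to decrease their dose", and this goes on "by 1 capsule daily until they tolerate the study drug".
- **Section 7.1.** A checklist rating of 1 (mild) leads to no action. A rating of 2 or 3 that is above baseline, and that the Principal Investigator and/or the Independent Clinical Monitor consider at least possibly related, leads to a discussion with the participant (and the parent or guardian of a minor) to "make a joint decision about the risks versus benefits of staying at the same dose versus decreasing the dose".

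No section says which of the three prevails.

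**The concern.** Under Section 1.1 the counted event is the reduction itself (or a discontinuation), not the symptom behind it. If three sections answer differently when a reduction is made, the same participant with the same symptom may or may not add to the count, depending on which section the staff apply. Arms are small and the limit is a proportion, so the count that separates a qualifying dose from a failing one is a matter of single participants. What is at stake is whether a stated decision rule has a determinate answer. The statistical plan in Section 9.6 does not supply one: it compares rates of side effects and adverse events between groups and does not define the 20% count.

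**Working it through.** **Step 1. The triggers side by side.**

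| Element | Section 5.1 | Section 7, item 1 | Section 7.1 |
|---|---|---|---|
| Severity | none stated | bothersome | rating 2 or 3; no action at 1 |
| Relatedness | likely or probable | likely or probable | at least possible |
| Rise from baseline | not required | not required | required |
| Action | instructed reduction | instructed reduction | joint decision, reduction optional |
| Reduction stops when | effect absent (stated aim: tolerance) | drug tolerated | not stated |

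**Step 2. Two test cases.**

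- Mild, probably related effect: instructed reduction under 5.1; no action under 7.1; under 7 it depends on whether the effect is called bothersome. These cannot all be followed.
- Moderate effect above baseline, only possibly related: neither 5.1 nor 7 triggers a reduction; 7.1 may lead to one.

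**Step 3. The limit as a count.** The 20% is a set threshold with no derivation, so there is no plan figure to reproduce. The largest passing count is the whole-number part of 0.20 × n.

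- n = 12 (planned group size, Précis): 0.20 × 12 = 2.4. Two pass (2/12 = 16.7%) and three fail (3/12 = 25%).
- n = 15 (Section 4.3 allows up to 46 enrolled; 46/3 = 15.3): 0.20 × 15 = 3. Three pass (exactly 20%) and four fail (4/15 = 26.7%).

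**Step 4. Illustrative chance that a dose fails.** The documents give no reduction rate under any trigger, so each rate p below is an assumption. The 19% is the complement of the 81% without side effects that Section 5.1 cites from a published study; 9.5% is half of that. The chance is the exact binomial upper tail, P(X ≥ r), with r the smallest failing count.

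For n = 12, r = 3, p = 0.19: 1 − [0.81^12 + 12 × 0.19 × 0.81^11 + 66 × 0.19^2 × 0.81^10] = 1 − [0.080 + 0.225 + 0.290] = 0.406 (computed before the terms were rounded).

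| Assumed rate | n = 12, fails at 3 | n = 15, fails at 4 |
|---|---|---|
| 5% | 0.020 | 0.005 |
| 9.5% | 0.098 | 0.047 |
| 15% | 0.264 | 0.177 |
| 19% | 0.406 | 0.315 |
| 25% | 0.609 | 0.539 |
| 30% | 0.747 | 0.703 |

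The result moves with the reduction rate, which depends on the trigger, and with the denominator, which Section 1.1 does not fix beyond naming subjects at that dose.

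**The case against.** Several points on the other side are sound and limit what can be claimed.

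- *Section 7.1 as a mirror image of 5.1.* A reader might infer that a moderate, possibly related effect must be reduced under 7.1 and must not be under 5.1. The text supports neither half: 7.1 makes reduction optional, and 5.1 is silent on possibly related effects.
- *Absent versus tolerated.* Section 5.1 also states a goal of tapering to tolerance. Its stopping point is thus loosely worded and not plainly a rival to that in Section 7. The two stopping phrases still differ.
- *Section 7.2 as a cure.* It labels side effects as adverse events once they are confirmed to affect functioning significantly, and brings in the Independent Clinical Monitor on corrective measures, including dose decreases. If 5.1 is read that way, mild effects drop out of it. But Section 7.3 defines an adverse event as any untoward medical occurrence, so this is a possible reading and not a resolution.
- *The pointer in Section 1.1.* It names one section, 5.1, for the counted event. That helps, but the count depends on reductions actually made, and Sections 7 and 7.1 also govern those.
- *The limit as sole decider.* A reader might infer that the 20% rule alone settles dose superiority. It is one of two conditions, the other being the glutathione increase.
- *0.41 against 0.10 as the effect of choosing a section.* The documents do not support this. The 19% is any side effect in an outside study, with no relatedness condition, and 9.5% is assumed. The contrast is between two assumed rates, not two protocol triggers.
- *Bias between arms.* Staff are blinded, so inconsistent application should not systematically favour an arm. It can still shift the absolute count, which is what the limit uses.
- *Small arms.* Sensitivity to one participant comes from a 20% cut-off in a small group and would remain after any rewording. True; reconciliation makes the count determinate, not more precise.

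**Conclusion.** The point holds as an inconsistency between current sections that feeds a stated decision rule. For a mild, probably related effect, 5.1 and 7.1 cannot both be followed, and nothing gives precedence. For a moderate, only possibly related effect, a counted reduction may arise under 7.1 although neither 5.1 nor 7 triggers one. The size is one or two participants per dose: the step from pass to fail is 2 to 3 of 12, or 3 to 4 of 15. The failure probabilities rest on assumed rates and a common independent risk within a dose; they show sensitivity and are not forecasts. The documents do not show that either dose would fail, that an arm would be favoured, or that the limit alone picks the dose. This should be corrected, and no view is taken on which clinical rule is right.

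**What to change.** Reconcile Section 5.1, Section 7 item 1 and Section 7.1 into one trigger, covering severity, relatedness, change from baseline, and instruction or joint decision, and one stopping point for reduction. Apply it identically in all arms. The choice belongs to the sponsor and investigators.

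Then have Section 1.1 state, before unblinding, which reductions and discontinuations count toward the 20% limit, and whether the denominator is all participants randomized to the dose, those who took study drug, or those with complete data. If reductions were already made under different sections, list them blinded, with severity, relatedness and the section applied, so that the count can be made on one definition.

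The cost is protocol wording and staff retraining. No extra visits, procedures or participants are needed.
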